5.5 Registration Guidelines

- All the patients must be registered with the Investigator(s) prior to initiation of treatment.
- Forms A (registration) and B (consent) will be submitted.
- The registration desk will confirm all eligibility criteria and obtain essential information (including patient number).

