6.4 SBRT

SBRT screening and planning will be performed by radiation therapists, medical physicists, and oncologists. Treatment will be delivered by a 6MV/10MV linear accelerator at 4 weeks (or within 21-35 days) after TACE

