6.4.3 Dose Specifications

Treatment Schedule: Treatment will be delivered in 5 fractions. The time between fractions should be between 24 and 72 hours, with treatment delivered to all targets over 5 to 15 days.

Prescription Dose: Absorbed dose: 27.5 Gy - 50 Gy in 5 fractions. The prescription dose may be 50 Gy, 45 Gy, 40 Gy, 35 Gy, 30 Gy or 27.5 Gy in 5 fractions, based on normal tissue constraints. The minimal planned prescription dose to PTVs is 27.5 Gy. The dose to multiple PTVs may be different. The goal is to use the highest allowable prescription dose to the primary target, while respecting normal tissue constraints. Dose prescription is based on the volume of normal tissues irradiated (correlated with mean liver dose), as well as proximity of stomach, duodenum, small and large bowel (GI luminal structures) to the target volumes, as normal tissue constraints must be maintained in this study.

Dose Specification: The prescription isodose should encompass 95% of PTV. If there are multiple PTVs, each should be planned for one of the prescription doses listed above, with each specific covering isodose planned to encompass 95% of each PTV, with normalization to the PTV receiving the highest dose. The highest allowable doses to the target volumes that maintain normal tissue constraints should be used. A goal is that 100% of the CTV is encompassed by the prescription dose.

Vascular tumor thrombosis (e.g., portal vein thrombosis) dose should be the same as the HCC prescription dose. However, lower doses are acceptable if required to maintain normal tissue limits, since the cancer density may be lower than parenchymal HCC.

Dose prescription based on mean liver dose (MLD)

| Prescription dose | Liver – GTV mean dose | |
|-------------------|-----------------------|-------------|
| | Ideal | Acceptable |
| 50Gy | ≤13Gy | 13-13.2Gy |
| 45Gy | ≤13Gy | 15-15.2Gy |
| 40Gy | ≤15Gy | 15-15.2Gy |
| 35Gy | ≤15.5Gy | 15.5-15.7Gy |
| 30Gy | ≤16Gy | 16-16.2Gy |
| 27.5Gy | ≤17Gy | 17-17.2Gy |

Organ-at-risk (OAR) dose constraints

Compliance Criteria:

| | Ideal | Acceptable |
|-------------------------------------------------------|-------|-----------------|
| Priority 1: Mandatory dose constraints | | |
| Stomach, small intestine, duodenum: Max (to 0.5cc) | 30Gy | >30Gy but ≤32Gy |
| Large bowel, oesophagus: Max (to 0.5cc) | 32Gy | >32Gy but ≤34Gy |
| Spinal cord + 5mm: Max (to 0.5cc) | 25Gy | >25Gy but ≤28Gy |

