6.5 Checkpoint Inhibitor: Avelumab

Avelumab will be started 14 days (or 14-18 days) upon completion of SBRT.

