7.5 Criteria for Removal From Protocol Treatment

- Disease progression
- Inter-current disease that would affect assessments of clinical status to a significant degree, require discontinuation of drug, or both
- Unacceptable toxicity
- The patient may withdraw from treatment at any time for any reason. The reason should be recorded. Follow-up will be continued for all consenting patients per standard clinical procedures, including regular follow-up visits, clinical and laboratory assessments for up to 5 years

- Avelumab treatment for maximum of 2 years

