8.3 Early Stopping Rule

Excessive toxicity will be monitored, which includes: (a) grade 4 or 5 hepatic; (b) grade 4 or 5 gastrointestinal; (c) grade 4 thrombocytopenia associated with any bleeding or grade 5 thrombocytopenia; (d) any grade 5 treatment-related adverse event. Assuming no more than a 10% rate of the above AEs on TACE, SBRT, or Avelumab alone, the increase to a rate of 30% or greater in the studied treatment will be considered unacceptable, and the study will be stopped prematurely. Upon the recruitment of these 33 patients, if 14 or more patients had treatment-related SAE, the study will be stopped. The corresponding lower bound of exact one-sided 90% confidence interval is 30.5%. The table below shows the stopping guideline scenarios for the first 8, 16 and 24 patients. For example, the study will be stopped when 11 of the first 24 patients develop an acute toxicity. The upper bound for the confidence intervals is 100%.

| Number of patients with serious adverse event | Number of patients enrolled | Lower bound of exact one-sided 90% confidence interval |
|-----------------------------------------------|-----------------------------|--------------------------------------------------------|
| 5 | 8 | 34.46% |
| 8 | 16 | 31.78% |
| 11 | 24 | 31.48% |

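### The toxicity stopping rule in 8.3 does not say that its boundaries stay in force after enrolment, and it counts different events from those its 10% and 30% rates describe

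*Protocol*

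**What the plan says.** Section 8.3 lists the excessive toxicities to be monitored: (a) grade 4-5 hepatic, (b) grade 4-5 gastrointestinal, (c) grade 4 thrombocytopenia with bleeding, or grade 5, and (d) any treatment-related grade 5 event. The reference rate is attached to that list: "Assuming no more than a 10% rate of the above AEs on TACE, SBRT, or Avelumab alone". A rise to 30% or more is called unacceptable.

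The final boundary reads: "Upon the recruitment of these 33 patients, if 14 or more patients had treatment-related SAE, the study will be stopped". A table headed by number of patients enrolled gives 5 of 8, 8 of 16 and 11 of 24, counted as serious adverse events. The worked example uses a third term: "the study will be stopped when 11 of the first 24 patients develop an acute toxicity".

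The timing of treatment is set elsewhere in the protocol:
- Section 5.5: "All the patients must be registered with the Investigator(s) prior to initiation of treatment".
- Section 6.4: SBRT is given "at 4 weeks (or within 21-35 days) after TACE".
- Section 6.4.3: five fractions, "with treatment delivered to all targets over 5 to 15 days".
- Section 6.5: "Avelumab will be started 14 days (or 14-18 days) upon completion of SBRT".
- Section 7.5: "Avelumab treatment for maximum of 2 years".
- Section 7.1: safety follow-up runs to 90 days after the last avelumab dose because immune toxicity can be delayed.

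**The concern.** There are two weaknesses in the same rule.

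**When the count is taken.** The last boundary is tied to a recruitment date and uses the past tense. Registration comes before any treatment, so a literal count is made before the 33rd patient has had avelumab and while others may still be on it. Later events would never enter it. The interim rows carry the same ambiguity at smaller numbers.

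**What is counted.** The 10% and 30% rates belong to list (a)-(d), but the counts are described in three other ways. Under section 7.7.2 any hospitalisation makes an event serious, so a grade 3 event outside the list could count towards 14. Conversely, a grade 4 laboratory hepatic event on the list need not be serious. Two people applying the rule to the same data could reach different totals.

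At stake is whether a combination with an unacceptable toxicity rate could pass the rule only because the count came early or used another event.

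**Working it through.** **1. The plan's own figures.** The exact one-sided 90% lower bound for r events in n patients is the 10th percentile of Beta(r, n - r + 1).

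| r/n | Recomputed | Protocol |
|---|---|---|
| 5/8 | 34.46% | 34.46% |
| 8/16 | 31.78% | 31.78% |
| 11/24 | 31.48% | 31.48% |
| 14/33 | 30.53% | 30.5% |

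At 13/33 the bound is 27.77%, so 14 is the smallest count of 33 whose bound exceeds 30%. The boundaries are sound.

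**2. Time from TACE to first avelumab.** Shortest: 21 + 5 + 14 = 40 days. Longest: 35 + 15 + 18 = 68 days. Registration is earlier still.

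**3. Patients not yet on avelumab at a literal final count.** The protocol gives no accrual period, so I assume even accrual over T = 12, 24 or 36 months, with TACE on the day of recruitment. The spacing is T/32 months, or about 11, 23 or 34 days. Patients recruited less than 40 to 68 days earlier number 4-6, 2-3 and 2 of 33.

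**4. The 14-of-33 look alone.** With complete data, P(X >= 14) for n = 33 is 0.088, 0.453 and 0.852 at true rates of 30%, 40% and 50%. For the literal count, patient i joins at T(i - 1)/32 and events fall evenly over the first W months. The share of risk seen is then min(1, (T - t_i)/W), and the count is a sum of unequal binary variables (Poisson-binomial, exact). At a true 40%:

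| W | T = 12 | T = 24 | T = 36 |
|---|---|---|---|
| 3 months | 0.21 | 0.31 | 0.35 |
| 6 months | 0.07 | 0.21 | 0.28 |
| 12 months | 0.002 | 0.07 | 0.16 |

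**5. The whole rule.** With all four boundaries standing and data complete, an exact binomial recursion over the looks gives stopping probabilities at a true 40% of 0.1737 + 0.1539 + 0.1059 + 0.1098 = 0.543. The first three alone give 0.433. The literal readings were simulated (200,000 trials, W = 6 months). Chance of any stop at a true 40%:

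| Reading | T = 12 | T = 24 | T = 36 |
|---|---|---|---|
| All looks are single snapshots | 0.08 | 0.24 | 0.32 |
| Interim looks stand, final look is a snapshot | 0.43 | 0.44 | 0.46 |
| All four stand | 0.54 | 0.54 | 0.54 |

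**6. The cost of standing boundaries.** With all four in force the chance of stopping is 0.0005 at a true 10%, 0.018 at 20% and 0.16 at 30%. With the first three alone standing it is 0.0005, 0.0165 and 0.131. With snapshots throughout it is below 0.0001 at 10%, at most 0.003 at 20% and 0.007-0.059 at 30%.

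**The case against.** A reader might infer that toxicity monitoring ends at the 33rd recruitment. The protocol does not say that. Section 8.3 gives monitoring no end date, and its example, "the study will be stopped when 11 of the first 24 patients develop an acute toxicity", reads as a rule about a group of patients whenever their events occur. On that reading the interim boundaries already stand and the gain from the fix is about 0.08 to 0.11 (0.54 minus 0.46 or 0.43). The much larger gap needs every look to be a snapshot, which sits badly with the example. This part of the objection stands and sets the priority.

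Several other limits also stand:
- Accrual and event timing are assumed. Section 6.4.4 places radiation-induced liver disease within about three months, so the 3-month row may suit TACE and SBRT toxicity better than the lower rows.
- Section 8.2 allows 10% withdrawal before treatment. If only about 30 of the 33 are treated, P(X >= 14) at 40% is 0.285 even with complete data.
- Once accrual closes no new patient is exposed. Sections 6.5.6 and 7.5 already take patients with grade 4 and most grade 3 avelumab reactions off the drug. It would be wrong to infer that patients are unprotected, although those rules do not test the cumulative rate.

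It can also be said that when a tally is updated is a matter for the statistical analysis plan. That would answer a silence, but here the protocol itself fixes the trigger and names the event in conflicting ways.

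**Conclusion.** The point holds as a defect of wording in a safety rule. The final boundary is tied to a recruitment date that precedes avelumab in the last patients, the interim rows share the ambiguity, and the event counted is not the one to which the 10% and 30% rates refer. The document does not support reading this as a miscalculated boundary or as proof that monitoring stops.

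That a count before exposure is complete can only miss events needs no assumption. The size does. At a true 40%, with a 6-month event spread and accrual over 12 to 36 months, making all four boundaries stand raises the chance of any stop from 0.43-0.46 to 0.54 if the interim looks already stand. If every look is a snapshot, the rise is from 0.08-0.32 to 0.54. Low priority, but cheap to repair.

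**What to change.** In section 8.3:
- State that 5/8, 8/16, 11/24 and 14/33 apply to the first 8, 16, 24 and 33 patients. Recheck them at each new qualifying event, including after accrual closes, until the last patient is 90 days past the last avelumab dose.
- Say that after accrual closes, stopping means no further avelumab pending review.
- Use one qualifying event throughout: a patient's first event from list (a)-(d). If non-fatal grade 4 immune-related events such as myocarditis or pneumonitis should count, add them to the list by name.
- Leave relatedness as the list has it, in item (d) only, unless the sponsor decides otherwise and says so.

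The boundary numbers do not change, and no new committee or data collection is needed.

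Costs:
- With all four boundaries standing, the chance of stopping is about 0.0005 at a true 10%, 0.018 at 20% and 0.16 at the 30% that the protocol calls unacceptable.
- Counting the list in place of all treatment-related SAEs drops serious events outside it, which lowers the chance of crossing. The sponsor should accept that knowingly.
- A longer window brings more late events whose cause must be judged against the underlying liver disease. Section 7.7.6 already records causality for TACE, radiotherapy and avelumab.

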8.2 Sample Size Calculation

H0: The null hypotheses of no difference in the number of patients who can undergo surgery: similar to the historical result of QMH, 5% of patients can undergo surgical intervention after TACE.

H1: The alternative hypotheses of treatment efficacy: the experimental treatment would result in 20% of study population who can undergo surgical resection after treatment response.

To detect 15% of differences from 5% to 20% in the number of patients proceeding to surgery, with Type I error of 0.05 and 80% power, assume 10% patients who have withdrawn may withdraw consent and patients who cannot be contacted during survival follow-up period, withdrawn subjects are only to before starting their protocol treatment. Patients will not be replaced once their protocol treatment started. The target accrual is 33 patients. Simon's two-stage optimal design will be used. In the first stage ten patients will be enrolled. If at least one is amenable to curative surgical intervention, the study can proceed to the second stage and an

additional 19 patients could be recruited. If at least 4 of the total 29 patients **are amenable to curative surgical intervention**, the treatment will be considered worthy of further investigation.

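### The toxicity stopping counts in Protocol 8.3 are correct, but none is given between 8, 16, 24 and 33 patients; applying the plan's own criterion at each new event would be a cheap improvement

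*Protocol*

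**What the plan says.** Section 8.3 of the protocol takes a 10% rate of the listed events as the reference ("Assuming no more than a 10% rate of the above AEs on TACE, SBRT, or Avelumab alone") and sets the limit as follows: "the increase to a rate of 30% or greater in the studied treatment will be considered unacceptable, and the study will be stopped prematurely".

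The counts come in two places. The table is introduced by "The table below shows the stopping guideline scenarios for the first 8, 16 and 24 patients" and lists 5 of 8, 8 of 16 and 11 of 24, with exact one-sided 90% lower bounds of 34.46%, 31.78% and 31.48%. The text adds the last one: "Upon the recruitment of these 33 patients, if 14 or more patients had treatment-related SAE, the study will be stopped", with a bound of 30.5%. One row is also put into words: "For example, the study will be stopped when 11 of the first 24 patients develop an acute toxicity".

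Section 8.3 gives no count for any other number of patients. It does not say that the lower bound is to be checked after each patient or event, and it describes no pause in accrual at or between the looks.

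**The concern.** The printed counts imply a criterion: stop when the exact one-sided 90% lower bound on the event rate passes 30%. That criterion can be met at any number of patients, but the plan names a count at only four, which lie 8 to 9 patients apart. Between them the data can give stronger evidence of excess toxicity than the evidence that stops the study at a printed look, and nothing written obliges anyone to act on it.

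The matter has some weight because the monitored events include grade 5 events and because this is the protocol's only study-level toxicity count. The two-stage rule in 8.2 looks at surgery alone. The check at 33 comes when recruitment is complete, so it can spare nobody enrolment. In practice three looks limit exposure.

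**Working it through.** **Inputs.** From 8.3: reference rate 10%, unacceptable rate 30%, stopping counts 5/8, 8/16, 11/24 and 14/33, exact one-sided 90% bounds. From 8.2: "The target accrual is 33 patients". An event below means whichever event 8.3 intends to count.

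**Step 1: reproduce the plan's bounds.** For x events in n patients the exact lower bound L solves P(X ≥ x | n, L) = 0.10, so L is the 0.10 quantile of a Beta(x, n − x + 1) distribution.

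| n | printed count | L | L with one event fewer |
|---|---|---|---|
| 8 | 5 | 34.46% | 23.97% |
| 16 | 8 | 31.78% | 26.29% |
| 24 | 11 | 31.48% | 27.72% |
| 33 | 14 | 30.53% | 27.77% |

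All four printed figures reproduce. Each count is the smallest at its n with L above 30%.

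**Step 2: the same bound between looks.** These outcomes can be reached without having met a printed count at a look:

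- 4/8 continues (23.97%). Three further events in a row give 7/11, with L = 40.1%. If the next five patients have none, the result is 7/16 (26.29%), which also continues.
- 7/16 continues. Three further events in a row give 10/19, with L = 35.8%.
- 10/24 continues. Three further events in a row give 13/27, with L = 34.5%.
- Before the first look, 4/5 has L = 41.6% and can become 4/8, which continues.

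**Step 3: the smallest count with L > 30% at every n from 8 to 33.** 5 at 8–9; 6 at 10–11; 7 at 12–14; 8 at 15–16; 9 at 17–19; 10 at 20–22; 11 at 23–25; 12 at 26–27; 13 at 28–30; 14 at 31–33. The printed counts are the entries at 8, 16, 24 and 33.

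**Step 4: operating characteristics.** Let f_n(k) be the probability that the study is still open after n patients with k events. Then f_n(k) = (1 − p)·f_{n−1}(k) + p·f_{n−1}(k − 1), and states with k at or above the count for n are removed as stops. P(stop) is the total removed. The mean number treated is the sum over n = 1 to 33 of the probability of still being open before patient n. The assumptions are a constant event probability p, each outcome known before the next patient is treated, and a maximum of 33.

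| True rate | P(stop), printed looks | P(stop), every n from 8 | Mean treated, printed looks | Mean treated, every n from 8 |
|---|---|---|---|---|
| 10% | 0.05% | 0.11% | 33.0 | 33.0 |
| 20% | 1.8% | 3.2% | 32.7 | 32.3 |
| 30% | 16.1% | 21.7% | 30.5 | 29.0 |
| 40% | 54.3% | 60.8% | 25.1 | 22.0 |
| 50% | 88.6% | 90.9% | 18.0 | 14.8 |

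Of the 16.1% at a 30% rate, 13.1 percentage points arise at the looks before 33. The rest arises at 33, when all patients are already in.

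**Step 5: two sensitivity checks.** First, suppose the printed rule stops as soon as the next look's count is reached, without waiting for that look. Its means become 24.47 at 40% and 16.84 at 50%. The savings are then 24.47 − 22.02 = 2.45 and 16.84 − 14.76 = 2.08 patients, instead of 25.09 − 22.02 = 3.07 and 18.01 − 14.76 = 3.25. Second, starting the extended rule at the 4th patient gives means of 20.2 and 12.7, but false stopping rises to 0.47% at a 10% rate and 5.3% at 20%.

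**The case against.** The strongest reply is that nothing here is wrong. Looks at set intervals are a legitimate phase II choice, and every printed figure is correct. That stands, and it is why the point is an improvement and no more.

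A second reply is that the table only illustrates continuous monitoring: it shows scenarios, one row is given as an example, and the 30% limit is not tied to four looks. The wording allows this. But the lower-bound criterion is never written as a rule for other numbers of patients, so no count could be enforced there. If continuous monitoring is what is meant, the fix merely writes it down.

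Third, stopping when 11 of the first 24 have an event can be read as stopping at the 11th event. On that reading the savings are the smaller ones in step 5.

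Fourth, toxicity here is delayed. SBRT follows TACE by 21 to 35 days (6.4) and is given over 5 to 15 days (6.4.3), and avelumab starts 14 to 18 days after it (6.5). Avelumab therefore begins 21 + 5 + 14 = 40 to 35 + 15 + 18 = 68 days after TACE and may run for two years (7.5). If accrual outpaces ascertainment, the savings shrink. The delay affects both rules and does not argue for leaving the gaps.

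Fifth, any starting point is a choice. The criterion is already crossed at 2/2 (31.6%), and a very early start adds most of the false stopping. Starting at the plan's own first look avoids this.

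**Conclusion.** The point holds as a cheap improvement. The counts in 8.3 are correct, but they leave gaps in which stronger evidence than the plan's own stopping evidence need not stop the study. Filling the gaps from the 8th patient treats about 3 fewer patients on average at true rates of 40% and 50%, or 2 to 2.5 fewer if the printed rule already stops when the next look's count is reached. The cost is a false-stop probability that stays near 0.1% at the 10% reference rate and rises from 1.8% to 3.2% at 20%. These figures assume a constant event rate and immediate ascertainment.

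Three stronger readings are not supported:

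- A reader might infer that the stopping table is miscalculated or contradicts itself. It does not; all four bounds reproduce.
- A reader might infer that patients have no other numeric protection. Sections 6.3.3, 6.4.5, 6.4.6 and 6.5.6 hold or end treatment for the individual patient, and 7.7.7 sets a reporting deadline for serious events. What is missing is a study-level count between looks.
- A reader might infer that more frequent checks make the rule sensitive at 30%. They do not: even then the study fails to stop about 78% of the time at that rate (100 − 21.7 = 78.3%), because of the 90% lower-bound criterion itself, which this change keeps.

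**What to change.** In 8.3, keep the criterion and the four printed counts and make three additions:

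1. State the criterion: the smallest count whose exact one-sided 90% lower bound exceeds 30%, checked at each new event.
2. State the minimum number of patients from which it applies, for example the 8th, which is the plan's own first look.
3. Print the full list of counts: 5 in 8–9 patients; 6 in 10–11; 7 in 12–14; 8 in 15–16; 9 in 17–19; 10 in 20–22; 11 in 23–25; 12 in 26–27; 13 in 28–30; 14 in 31–33.

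The section should also report the resulting stopping probabilities and say how patients still under observation enter the count. An earlier start would save more patients under excess toxicity at the price of the higher false-stop figures in step 5; the sponsor should choose and state the reason.

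The cost is a longer table and a running tally of events already recorded under 7.7.6. No extra patients or procedures are needed.

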9. ETHICAL, REGULATORY & STUDY OVERSIGHT CONSIDERATIONS

9.1 Responsibilities of the Investigator(s)

The Investigator(s) undertake(s) to perform the clinical study in accordance with this clinical study protocol, ICH guideline for Good Clinical Practice (GCP) (ICH E6 R2 Step 4) approved on November 9, 2016) and applicable regulatory requirements in Hong Kong. These documents state that the informed consent of the subjects is an essential precondition for participation in the clinical study.

